15.6 Power analysis

Decision thresholds and power are based on a preliminary analysis of 147 D-dimer measurements taken on 41 COVID-19 patients admitted to Michigan Medicine. Using variance

components regression on log-transformed D-dimer levels, we found that the intraclass correlation coefficient (ICC) for participants (between-participant variance to total variance) was 0.77 in a model controlling for days since admission and ICU status (binary) as fixed effects. ICU status serves as a proxy for case severity. An increasing trend in D-dimer levels (~13% per day) was common to both groups. The moderately high ICC reflects the contributions of around 90% within-participant variation (day-to-day) relative to around 300% between-participant variation. Thus, D-dimer levels largely behave as a stable participant-level trait that may indicate the underlying extent of disease. Defining the endpoint in terms of the least squares slope of D-dimer level using up to 7 measurements reduces the impact of daily D-dimer fluctuations and thereby increases statistical power.

To assess power for the proposed design, we used a simulation approach matching the patient population characteristics learned from the analysis of preliminary data reported above. For power simulation, the ICC was set to 0.7, somewhat lower than the observed ICC of 0.77, in order to provide a margin for uncertainty in the pilot results. Power is based on a 13% daily increase in D-dimer levels for untreated participants, as observed in preliminary analysis. We posited a 50% reduction in the growth rate for the 100 mg dose. Using 2 arms with 40 participants per arm (100 participants in all), power is 0.91 for comparing the dipyridamole-treated participants to the controls. However, the standard of care treatment has changed with introduction of anti-inflammatory steroids which suggests an increase in sample size may be necessary to complete the study.

15.7 Sample Size and Randomization

We will enroll 100 participants to complete this study based on the power calculation. Patients will be recruited for this study and randomized in a 1:1 ratio using stratified random blocks. This study is a proof-of-concept multi center, single-blinded, randomized, controlled trial to evaluate the effectiveness of dipyridamole to reduce progressive coagulation dysfunction associated with coronavirus infection.

16 DATA COLLECTION, RETENTION AND MONITORING

16.1 Data Collection Instruments

The Site-Investigator or trained delegates will prepare and maintain adequate and accurate source documents designed to record all observations and other pertinent data for each participant treated with the study drug.

Study personnel will enter data from source documents corresponding to a participant's visit into secured, central databases. Participants will not be identified by name in the study database or on any study documents to be collected by the designee but will be identified by a participant number and initials.

If a correction is made on a paper source document, the study staff member will line through the incorrect data, write in the correct data and initial and date the change.

The site investigator is responsible for all information collected on participants enrolled in this study. All data collected during the course of this study must be reviewed and verified for completeness and accuracy by the investigator.

16.2 Data Management Procedures

The data will be entered into a HIPAA compliant database.

16.3 Data Quality Control and Reporting

After data have been entered into the study database, a system of computerized data validation checks will be implemented and applied to the database on a regular basis.

16.4 Availability and Retention of Investigational Records

The Site Investigator will make study data accessible to the IRB and Regulatory Agency (e.g., FDA) inspectors upon request. A file for each participant will be maintained that includes the signed Informed Consent with HIPAA Authorization and source documentation related to that participant. The Site Investigator will ensure the reliability and availability of source documents.

All study documents (participant files, signed informed consent forms, copies of source documents, etc.) will be kept secured for a period of 7 years following the completion of the study.

16.5 Monitoring

The PI will be primarily responsible for monitoring data integrity. Monitoring is intended to protect participants' rights and safety, and to ensure the integrity and quality of the data collected. The PI will ensure that all relevant IRBMED and FDA policies, procedures, and stipulations are followed by the study team. This study will be monitored by MICHR monitor. Monitoring will be conducted prior to the initiation of study enrollment and throughout the life cycle of the study.

16.6 Participant Confidentiality

In order to maintain participant confidentiality, only a participant study ID number and participant initials will identify all study participants on source documents and other documentation submitted to the IRB. Bio specimen samples that will be analyzed in a collaborator's research laboratory will only contain the participant study ID number.

17 ADMINISTRATIVE, ETHICAL, REGULATORY CONSIDERATIONS

To maintain confidentiality, all laboratory specimens, evaluation forms, reports and other records will be identified by a coded number and initials only. All study records will be kept in a locked file cabinet and code sheets linking a participant's name to a participant identification number will be stored separately in another locked file cabinet. Clinical information will not be released without written permission of the participant, except as necessary for monitoring by the FDA.

The Site Investigator will also comply with all applicable privacy regulations (e.g., Health Insurance Portability and Accountability Act of 1996, EU Data Protection Directive 95/46/EC).

17.1 Protocol Amendments

Any amendment to the protocol will be written by the Sponsor, National-Investigator or designee. Protocol amendments will not be implemented without prior written IRB approval except as necessary to eliminate immediate safety hazards to participants. A protocol amendment intended to eliminate an apparent immediate hazard to participants may be implemented immediately, provided the IRBs are notified within five working days.

17.2 Institutional Review Boards

The protocol and consent form will be reviewed and approved by the Institutional Review Boards at each institute prior to study initiation. Serious adverse experiences regardless of causality will be reported to the IRB in accordance with the standard operating procedures and policies of the IRB, and the Site-Investigator will keep the IRB informed as to the progress of the study.

Any documents that the IRB may need to fulfill its responsibilities (such as protocol, protocol amendments, consent forms, information concerning patient recruitment, payment or compensation procedures, or other pertinent information) will be submitted to the IRB. The IRB written unconditional approval of the study protocol and the informed consent form will be in the possession of the Site-Investigator before the study is initiated.

Protocol and/or informed consent modifications or changes may not be initiated without prior written IRB approval except when necessary to eliminate immediate hazards to the participants or when the change(s) involves only logistical or administrative aspects of the study. Such modifications will be submitted to the IRB and written verification that the modification was submitted and subsequently approved will be obtained.

The IRB will be informed of revisions to other documents originally submitted for review; serious and/or unexpected adverse experiences occurring during the study in accordance with the standard operating procedures and policies of the IRB; new information that may affect adversely the safety of the participants of the conduct of the study; an annual update and/or request for re-approval; and when the study has been completed.

17.3 Informed Consent Form

The Investigator or designee will prepare the informed consent form containing HIPAA authorization and the investigator will provide the documents to the IRB. The consent form generated by the Site-Investigator will be approved by the IRB. The Site-Investigator will store an IRB-approved copy of the Informed Consent Form in the study regulatory binder.

A properly executed informed consent will be obtained from each participant prior to entering the participant into the trial. Information will be given in both oral and written form and participants will be given ample opportunity to inquire about details of the study. A copy of the

signed consent form will be given to the participant and the original will be maintained with the participant's records.

APPENDIX 1. Schedule of Study Events

See attached SOE document

APPENDIX 2. Summary of Changes

4.1 Preface

This Statistical Analysis Plan (SAP) describes statistical methods and analyses for the DICER study. This document should be read in tandem with the DICER Study Protocol version 5.0, dated November 23, 2020.

Immune hyperactivation and thrombophilia appear to predict worse outcomes in individuals with COVID-19. The majority of hospitalized patients infected with COVID-19 develop coagulation dysfunction as indicated by elevated levels of D-dimer protein, which predicts acute respiratory distress syndrome (ARDS), venous thromboembolism, and mortality. Dipyridamole is an adenosinergic drug with a favorable safety profile that reduces thrombosis, reduces immune hyperactivation, and directly inhibits SARS-CoV-2 virus replication. A small clinical trial of dipyridamole in 31 patients with moderate- and severe-COVID-19 showed safety of dipyridamole and efficacy in reducing D-dimer levels, and a trend toward improved clinical outcomes (Liu et al, 2020).

The intent of this proof-of-concept study is to evaluate whether the drug dipyridamole will reduce D-dimer elevation in participants with moderate COVID-19 as measured by: increase in D-dimer, respiratory status, ventilation and mortality, and ICU admission. If this novel approach is effective in reducing the progression of D-dimer elevation, it will inform a larger, multi-center trial to determine efficacy in preventing progression of moderate to severe COVID-19 infection. The result may broadly improve care of patients with coronavirus infection.

4.2 Scope of the Analyses

The purpose of this document is to describe primary and secondary statistical analyses to be conducted with regard to the efficacy and safety of dipyridamole versus placebo in the DICER clinical trial.

5 Study Objectives and Endpoints

5.1 Study Objectives

Due to changes in standard of care for COVID-19 patients, this study has two co-primary objectives, with the original secondary endpoint being elevated to a co-primary endpoint. The first and original primary objective of this study is to compare the effect of dipyridamole vs. placebo on plasma D-dimer changes in patients with moderate COVID-19. The second primary objective, formerly a secondary objective, is to compare the effect of dipyridamole vs. placebo on a composite of clinical outcomes including death, survival time, days on mechanical ventilation, decrease in SpO₂/FiO₂ ratio, and cumulative COVID ordinal scores.

5.2 Endpoints

For convenience, we give names to the following times and time windows:

- Baseline or Day 1: Date of the first study drug administration
- Study Hospitalization: Day 1 through either Day 14 or hospital discharge, whichever is first
- Observation Period: The 28-day period following first study drug administration
- Study Duration: The period from baseline until 30 days after last study drug administration

If an endpoint is to be evaluated at all three of the above time points, we use the phrase ‘at any time point’.

Endpoints are presented in a numbered list to facilitate references to endpoints when conducting the final analysis.

5.2.1 Primary Endpoint

The first co-primary endpoint is increase in plasma D-dimer levels compared to baseline.

The second co-primary endpoint is a clinical hierarchical composite of:

- Time to death from any cause during study duration
- Number of days on mechanical ventilation during study hospitalization
- A dichotomized (yes/no) decrease in daily average SpO₂/FiO₂ ratio of at least 50 units relative to Day 1 at any time during the observation period
- Cumulative sum of COVID ordinal scores during study hospitalization

5.2.2 Secondary endpoints

1. Days alive and free of organ support, where:
 - Organ support is defined as receipt of invasive mechanical ventilation, vasopressor therapy, ECMO support, or dialysis
2. Individual components of composite endpoint

5.2.3 Safety Endpoints

3. During the observation period, incidence of bleeding associated with: (i) a decrease in the hemoglobin level of at least 2 g per deciliter, (ii) transfusion of at least 2 units of blood, (iii) occurrence in a critical site, or (iv) contributing to death
4. Incidence of serious adverse events (SAEs) during study duration
5. Incidence of hypotension with systolic blood pressure below 90 mmHg and requiring a 1-liter IV fluid bolus during study hospitalization

5.2.4 Exploratory Endpoints

Based on consultation with the DICER researchers, SABER will only analyse a subset of the exploratory endpoints specified in the original protocol. Numbers in the following list (e.g. #17) refer to Section 3.4 Exploratory Outcomes in the protocol, version 5.0.

6. Blood Oxygenation
 - Time to increase in daily average SpO₂/FiO₂ ratio of at least 50 units relative to Day 1 during the observation period (#17)
7. Ventilation
 - Initiation of mechanical ventilation or ICU care during observation period (yes/no) (#6)
 - Initiation of mechanical ventilation during observation period (yes/no) (#11)
 - Initiation of ICU care during observation period (yes/no)
8. Change from baseline at Day 5 for: C-reactive protein, LDH, ferritin, total leukocyte count, neutrophils, lymphocytes, and platelet count in the blood (#4)
 - Daily changes from Day 1 in neutrophils and lymphocytes
9. Hospitalization
 - Time to hospital discharge (#7)

- Incidence of hospital readmission during study duration (#30)
- 10. Supplemental Oxygen
 - Proportion of surviving patients still requiring supplemental oxygen at the end of the observation period (#8)
 - Number of days on supplemental oxygen during observation period (#9)
- 11. Imaging: Proportion of study population with each of the following:
 - Arterial or venous thromboembolism diagnosed by imaging study during study duration (#25)
 - Venous thrombosis diagnosed by imaging study during study duration (#26)
 - Arterial thrombosis diagnosed by imaging study during study duration (#27)
- 12. Change from Day 1 in daily average glomerular filtration rate (GFR) during observation period, assessed daily through Day 5 (#28)
- 13. An alternative version of the second co-primary endpoint decision-rule:
 - Time to death from any cause during study duration
 - Number of days on mechanical ventilation during study hospitalization
 - A dichotomized (yes/no) decrease in daily average $\text{SpO}_2/\text{FiO}_2$ ratio of at least 50 units relative to enrollment date at any time during the observation period
 - A dichotomized (yes/no) increase in Ordinal Score at any time relative to enrollment
 - Analyze dichotomized (yes/no) increase in Ordinal Score at any time relative to enrollment as a standalone endpoint

Additional analyses done separately from SABER (to be done at a future date):

- 14. A dichotomized (yes/no) decrease for patients with elevated Day 1 neutrophil activation during study hospitalization, where elevated is defined as $> 2 \text{ SD}$ above established healthy controls (#22)
- 15. A dichotomized (yes/no) decrease for patients with elevated Day 1 inflammatory, anti-inflammatory, and other cytokines in blood during study hospitalization, where elevated is defined as blood defined as $> 2 \text{ SD}$ above established healthy controls (#23)
- 16. A dichotomized (yes/no) decrease for patients with elevated Day 1 coagulant and anticoagulant cytokines in blood during study hospitalization, where elevated is defined as blood defined as $> 2 \text{ SD}$ above established healthy controls (#24)
- 17. Gene expression, function, and activation of peripheral blood leukocytes following treatment on Days 1 or 5 (#29)

6 Study Methods

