3.4 Exploratory Outcomes

1. **Title:** C-reactive protein, LDH, ferritin, leukocyte count, platelet count in blood
Description: Improvement for participants with abnormal levels at day 1 (>standard laboratory cutoff)
Time Frame: Data gathered through 28 ± 1 day
2. **Title:** Incidence of mechanical ventilation or ICU care
Description: Incidence of mechanical ventilation initiation or ICU care
Time Frame: Data gathered through 28 ± 1 day
3. **Title:** Time to hospital discharge
Description: Time to hospital discharge will account for death and lost to follow up as a competing risk and censoring event, respectively.
Time Frame: Data gathered through 30 days after last study drug administration

4. **Title:** Proportion of participants requiring supplemental oxygen
Description: Incidence of participants alive without requirement for ongoing oxygen supplementation.
Time Frame: Data gathered through 28 ± 1 day
5. **Title:** Number of days of supplemental oxygen use
Description: Number of days of supplemental oxygen use
Time Frame: Data gathered through 28 ± 1 day
6. **Title:** Time to improvement in average daily oxygenation
Description: Time to first improvement in average daily SpO₂/FiO₂ ratio of 50 or greater compared to the nadir SpO₂/FiO₂ ratio
Time Frame: Data gathered through 28 ± 1 day
7. **Title:** Neutrophil activation studies
Description: Decrease for participants with elevated levels at day 1 (>2 SD above established healthy-controls)
Time Frame: Data gathered through day 14 ± 1 day
8. **Title:** Inflammatory, anti-inflammatory, and other cytokines and molecules in blood
Description: Increase or decrease for participants (>2 SD above established healthy-control mean)
Time Frame: Data gathered through day 14 ± 1 day
9. **Title:** Coagulant and anticoagulant cytokines and molecules in blood
Description: Increase or decrease for participants (>2 SD above established healthy-control mean)
Time Frame: Data gathered through day 14 ± 1 day
10. **Title:** Incidence of arterial or venous thromboembolism
Description: Arterial or Venous thromboembolism diagnosed by imaging study
Time Frame: Data gathered through 28 ± 1 day
11. **Title:** Incidence of venous thromboembolism
Description: Venous thrombosis diagnosed by imaging study
Time Frame: Data gathered through 28 ± 1 day
12. **Title:** Incidence of arterial thrombosis
Description: Arterial thrombosis diagnosed by imaging study
Time Frame: Data gathered through 28 ± 1 day

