6.3 Study Assessments

Table 1. Schedule of Events

Study Day	Screening Enrollment	Day 1	Days 3, 7, 11	Days 5, 9, 13	Even Days 2-12	Day 14	Day 28	Early Withdrawal	30 Days After Drug
Screening via chart review	X								
Screening for eligibility	X								
Informed consent	X								
Pregnancy test ^a	X								
Demographics		X							
Medical history		X							
Social history ^b		X							
Physical exam SOC review ^c		X							
Randomization	X								
Study drug administration		X	X	X	X	X			
Vitals/Oximetry SOC review ^c		X	X	X	X	X	X ^j	X	
Respiratory status SOC review ^c		X	X	X	X	X		X	
Clinical progress review		X	X	X	X	X		X	
Clinical care lab result review		X	X	X	X	X		X	
ECG clinical care data review ^d		X	X	X	X	X		X	
Chest imaging review ^d		X	X	X	X	X		X	
BMP ^e		X	X	X				X	
D-dimer ^e		X	X	X		X		X	
Ferritin ^e		X		X				X	
LDH ^e		X		X				X	
CRP ^e		X		X				X	
CBC w/ diff ^e		X	X	X		X		X	
FBN ^e		X	X	X		X		X	
PTT/INR ^e		X	X	X		X		X	
ABG ^d		X							
LFT ^e		X		X				X	
Research blood draw ⁱ		X ^f	X ^f	X ^f				X	
Concomitant meds/therapies		X	X	X	X	X	X ^g	X	
AE assessment		X	X	X	X	X	X ^g	X	X ^h

a Performed in subjects of child-bearing potential, if not already performed for clinical care reasons

b Social history including pregnancy history, tobacco and alcohol use

c Medical chart review for extraction of standard-of-care data.

d Only if performed while patient is inpatient/hospitalized for clinical care reasons. Data will be recorded.

e Lab results will be extracted from blood drawn for clinical care, whenever possible..

f Blood collection will be coordinated with blood draw for clinical care lab studies, whenever possible.

g Medical chart review for secondary endpoints will continue until Day 28.

h Chart review and phone call for AEs assessment until 30 days after last dose of study drug, maximum of 44 days from initial participation date.

i: Research lab draws on study days 3,5,9,11,13 will have +/- 1 day window.

Prior to conducting any study-related activities, written informed consent containing Health Insurance Portability and Accountability Act (HIPAA) authorization will be signed and dated by the participant.

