8.4 Missing Data

We anticipate three sources of missing response data in this study: missing data entries, loss to follow-up, and early hospital discharge. We will summarize missingness for primary study endpoints. In preliminary results, a large majority of patients have early hospital discharge.

For the primary response and other longitudinal analyses, we address missing response data through random coefficients regression, which incorporates missingness through the standard errors of subject-level trend estimates. This strategy assumes missing entries are missing at random and that missing entries from early termination or discharge would not differ from the trend in the observed data. For time-to-event responses, we address early termination and discharge by right-censoring.

The DICER team will review data to minimize missingness in sex, age, and baseline values. Following Schafer et al. (1997), if these variables are missing for more than 5% of patients, we will impute them using SAS PROC MI and PROC MIANALYZE if necessary. Otherwise, we will exclude missing records from the analyses.

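### SAP exploratory items 14–16 score each biomarker as a yes/no fall from a high Day 1 value, with no minimum fall, named draw or combining rule; a baseline-adjusted continuous change would use the same samples better

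*SAP*

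**What the plan says.** Three exploratory items in SAP 5.2.4 share one form. Item 14 is "A dichotomized (yes/no) decrease for patients with elevated Day 1 neutrophil activation during study hospitalization", item 15 is "A dichotomized (yes/no) decrease for patients with elevated Day 1 inflammatory, anti-inflammatory, and other cytokines in blood during study hospitalization", and item 16 is "A dichotomized (yes/no) decrease for patients with elevated Day 1 coagulant and anticoagulant cytokines in blood during study hospitalization". Elevated means more than 2 SD above healthy controls. That limit decides who enters the analysis; it does not say how far a value must fall.

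SAP 5.2 sets the window: "Study Hospitalization: Day 1 through either Day 14 or hospital discharge, whichever is first". Its length therefore differs by patient. Protocol 10.4, 10.6, 10.8, 10.10, 10.12 and 10.14 schedule post-baseline research blood on Days 3, 5, 7, 9, 11 and 13. SAP 8.4 adds: "In preliminary results, a large majority of patients have early hospital discharge". SAP 8.6.2.1 says most patients have left by Day 7, which leaves usually at most three later draws.

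Elsewhere the same list is specific. Item 8 fixes Day 5. Item 13 gives a 50-unit threshold and says the drop may occur at any time. SAP 10.4 analyses binary exploratory endpoints by logistic regression on treatment, sex and age, and change-over-time endpoints by the mixed model of SAP 10.1.

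The direction wording varies. The Protocol synopsis speaks of a decrease among patients with elevated baseline values. Protocol 3.4 items 8 and 9 say "Increase or decrease for participants (>2 SD above established healthy-control mean". SAP items 15 and 16 count only a decrease.

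Items 14–16 are to be analysed later, separately from the main statistical team's work.

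**The concern.** Three features combine. Selecting patients with high Day 1 values means that later values tend to be lower by regression to the mean. With no minimum fall, assay noise alone can produce a response. If one lower value at any draw is enough, each extra draw is another chance, and the number of chances is set by length of stay. The logistic model in SAP 10.4 has no term for the number of draws.

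Two things are at stake. A high background response rate in both arms leaves little room to show a drug effect. And if dipyridamole shortened stay, its own arm would have fewer draws and a lower response rate, so a clinical benefit would appear as a worse biomarker result.

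The SAP also scores a fall in anti-inflammatory or anticoagulant molecules in the same way as a fall in harmful ones, although Protocol 3.4 leaves the direction open for these panels.

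**Working it through.** The documents give no response rate, sample size or power for items 14–16, so there is no stated figure to reproduce.

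**Inputs from the documents.** Up to six later draws, usually at most three. The only correlation and trend figures are for D-dimer: a pilot ICC of 0.77 with 0.7 used for planning, about 90% within-patient variation, and a 13% daily rise (Protocol 15.6, SAP 7.1). They serve here as proxies.

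**Assumptions.** ICC 0.5 to 0.9; share of patients elevated 50% to 100%; within-patient SD on the log scale ln(1.9) = 0.64; no drug effect.

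**Step 1: flat marker, no selection, any draw counts.** The Day 1 value and k later values are exchangeable, so Day 1 is the lowest of the k + 1 values with probability 1/(k + 1). Hence P(at least one later value is lower) = k/(k + 1): 1/2 = 50%, 2/3 = 67%, 3/4 = 75%, and 6/7 = 86% for six draws. This holds whatever the variance.

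**Step 2: add selection.** For one later draw, with the upper half of Day 1 values eligible and correlation ρ, P(fall) = 1/2 + arcsin(√((1 − ρ)/2))/π.
- ρ = 0.77: 0.5 + arcsin(0.339)/π = 0.5 + 0.110 = 61%.
- ρ = 0.5: 0.5 + arcsin(0.5)/π = 0.5 + 0.167 = 67%.
- ρ = 0.9: 0.5 + arcsin(0.224)/π = 0.5 + 0.072 = 57%.

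**Step 3: more draws and a trend.** Simulation of 400,000 patients per scenario, with log value = patient level + trend × days since Day 1 + noise. Percentage with at least one later value below Day 1:

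| Scenario | 1 draw | 2 draws | 3 draws | 6 draws |
|---|---|---|---|---|
| Flat, no selection (exact) | 50 | 67 | 75 | 86 |
| Flat, 90% elevated, ICC 0.77 | 53 | 70 | 78 | 88 |
| Flat, 50% elevated, ICC 0.77 | 61 | 78 | 85 | 93 |
| Flat, 50% elevated, ICC 0.5 | 67 | 83 | 90 | 96 |
| Rising 13%/day, 90% elevated, ICC 0.77 | 42 | 53 | 57 | 60 |
| Rising 13%/day, 50% elevated, ICC 0.77 | 50 | 62 | 67 | 70 |
| Rising 13%/day, 50% elevated, ICC 0.5 | 55 | 68 | 73 | 76 |

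**Step 4: length of stay.** Flat marker, half elevated, ICC 0.7: three draws 86.5%, two draws 79.3%; 86.5 − 79.3 = 7.2 points, against the arm discharged sooner and with no marker effect.

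**Step 5: last-draw reading.** If only the last draw counts, a flat marker (ICC 0.77, half elevated) gives 61% at every number of draws. A marker rising 13% per day goes from 50% with one draw to 8% with six. The two readings therefore give very different endpoints.

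**Step 6: sensitivity lost.** Illustration: 30 elevated patients per arm, three later draws each, drug-related fall of 0.25, 0.5 and 0.75 SD at Days 3, 5 and 7, two-sided 0.05, 2,000 simulated trials. At ICC 0.77, power is about 18% for any decrease (Fisher's exact test) and about 84% for Day 5 change adjusted for Day 1. Keeping yes/no but fixing Day 5 gives about 46%, so naming the draw recovers only part of the loss. The order is the same at ICC 0.5 (about 4% against 59%) and ICC 0.9 (about 41% against 99%).

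**Step 7: would a size threshold be enough?** With an illustrative 30% minimum fall, any draw, flat marker and no selection, the no-effect rate still climbs from 35% with one draw to 72% with six. A threshold alone does not remove the dependence on stay.

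**The case against.** The strongest reply is that the figures depend on a reading the SAP does not state and on inputs it does not give. Items 14–16 do not say that a fall at any time counts, whereas item 13 does say so for its own endpoint. A reader might infer that the endpoints count any decrease, that most patients must respond, and that the rate saturates in both arms. The documents do not support that as a general statement. For a marker rising 13% per day with 90% of patients elevated, fewer than half respond with one draw. If nearly all patients exceed the 2 SD limit, selection adds only about 3 points to the flat-marker rate. Rates above 90% mostly need more draws than the usual three. The power illustration uses an assumed 30 patients per arm and an assumed effect, and gives every patient a Day 7 draw that many would not have. All this stands, and it limits the size of the claim.

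A reader might also infer that these are the only endpoints bearing on mechanism. They are not: D-dimer is co-primary, and items 8, 11 and 17 cover inflammatory markers, thromboembolism and leukocyte activation.

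Nor does the plan inflate type I error by itself. With equal stay, regression to the mean and the number of draws act alike in both randomised arms. Nothing in the documents shows that stay differs by arm. Finally, SAP 8.7 requires exploratory findings to be confirmed before reporting, so no trial decision turns on these items.

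What this reply does not answer is that the rule is open. Either reading keeps a regression-to-the-mean response in the selected patients and discards the size of the change.

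**Conclusion.** The point holds in a limited form. Items 14–16 leave the response undefined as to size, timing and combination of draws, and dichotomising loses information on either reading. On the any-draw reading, the no-effect rate for a flat marker is about 50–67% with one later draw and 75–90% with three (ICC 0.5–0.9, 50–100% elevated). For a marker rising 13% per day it is about 40–55% and 56–73% (50–90% elevated). The rise with stay belongs to the any-draw reading; for a flat marker it disappears if only the last draw counts. The bias of about 7 points arises only if the arms differ in stay, here by one draw for every patient. Otherwise the harm is lost sensitivity.

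The direction wording is a separate inconsistency that needs no assumption: the Protocol synopsis and Protocol 3.4 differ from each other, and the SAP follows the synopsis.

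This is a cheap improvement of low to moderate priority.

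**What to change.** Replace the yes/no decrease in items 14–16 with signed log change from Day 1. Analyse it with the mixed model of SAP 10.1 and 10.4 on actual sampling time, with the Day 1 log value as covariate, in mITT patients who have a Day 1 sample and at least one later sample. Report the Day 5 contrast between arms from that model. Keep the group above 2 SD as a descriptive subset, and do not label a direction as response for anti-inflammatory or anticoagulant molecules.

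State that patients discharged before any later draw contribute no change, and that the model assumes missing at random, as SAP 8.4 already does for longitudinal outcomes. Do not substitute an analysis of patients still present on Day 5: it would condition on remaining in hospital, which treatment may affect.

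Reconcile the direction wording in the Protocol synopsis, Protocol 3.4 items 8 and 9, and SAP items 15 and 16.

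The cost is wording only. The SAP defers these analyses to a future date, and no extra samples are needed. The small downside is that a log-scale change is less simple to report than a responder rate.
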